4.3 Blinded Assessment

The study team member will evaluate the images for signs of surgical site infection and will be blinded to the type of wound protector used intraoperatively. This will be done at regular intervals and in aggregate.

4.4 Data Recording

Data will be collected from EPIC by the study team. A secure REDCap database will be utilized to store the data. The following variables will be recorded:

A) Preoperative variables:

- Patient Demographics:
 - DOB, age at the time of surgery, gender, race, Height, weight and body mass index (BMI) at the time of surgery.
- American Society of Anesthesiologists physical status classification (ASA score).
- Preoperative diagnosis and patient's History of present illness.
- Adherence to SSI prevention bundle (elements defined above).
- Risk factors for SSI including nutritional status (represented by patient current weight) and immune status including WBC and differentials, history of smoking, and any other risk factors for SSI.

B) Intraoperative variables:

- Operating surgeon.
- Length of incision/wound.
- Surgical approach (open vs. laparoscopic vs transanal).
- Device deficiencies including (leaking of fluid, breakage of plastic sheath, ring malfunction in CleanCision wound protector).

C) Postoperative variables:

- In-patient Progress notes.
- The development of SSI per the criteria defined above along with any related investigation / clinical encounter needed for such diagnosis. The timing of SSI development.

4.5 Definitions

The World Health Organization (WHO) definitions of wound classifications and SSIs were adopted in this study. The WHO definitions are based on the Center for Disease Control and Prevention (CDC) National Healthcare Safety Network (NHSN). NHSN is the nation's most widely used healthcare-associated infection tracking system ¹⁴.

Surgical wound classification

1. Clean: An uninfected operative wound in which no inflammation is encountered and the respiratory, alimentary, genital, or uninfected urinary tracts are not entered. In addition, clean wounds are primarily closed and, if necessary, drained with closed drainage.
2. Clean-contaminated: Operative wounds in which the respiratory, alimentary, genital, or urinary tracts are entered under controlled conditions and without unusual contamination. Specifically, operations involving the biliary tract, appendix, vagina, and oropharynx are included in this category, provided no evidence of infection or major break in technique is encountered.
3. Contaminated: Open, fresh, accidental wounds. In addition, operations with major breaks in sterile technique (for example, open cardiac massage) or gross spillage from the gastrointestinal tract, and incisions in which acute, non-purulent inflammation is encountered including necrotic tissue without evidence of purulent drainage (for example, dry gangrene) are included in this category.
4. Dirty or infected: Includes old traumatic wounds with retained devitalized tissue and those that involve existing clinical infection or perforated viscera. This definition suggests that the organisms causing post-operative infection were present in the operative field before the operation.

Surgical Site Infections (SSI)*Superficial SSI*

A) An infection occurring within 30 days of the operative procedure (where day 1 = the procedure date).

B) AND involves only skin and subcutaneous tissue of the incision.

C) AND patient has at least one of the following:

- Purulent drainage from the superficial incision.
- Organisms identified from an aseptically-obtained specimen from the superficial incision or subcutaneous tissue by a culture or non-culture based microbiologic testing method which is performed for purposes of clinical diagnosis or treatment.
- Superficial incision that is deliberately opened by a surgeon or other designee and culture or non-culture based testing is not performed AND patient has at least one of the following signs or symptoms: pain or tenderness; localized swelling; erythema; or heat.
- Diagnosis of a superficial incisional SSI by the surgeon or other designee.

The following do not qualify as superficial SSI:

- Diagnosis/treatment of cellulitis (redness/warmth/swelling), by itself, does not meet criterion "d" for superficial incisional SSI. Conversely, an incision that is draining or that has organisms identified by culture or non-culture based testing is not considered a cellulitis.
- A stitch abscess alone (minimal inflammation and discharge confined to the points of suture penetration).

- A localized stab wound or pin site infection- Such an infection might be considered either a skin or soft tissue infection, depending on its depth, but not an SSI.

Deep SSI

A) An infection occurring within 30 days of the operative procedure (where day 1 = the procedure date).

B) AND involves deep soft tissues of the incision (for example, fascia and muscle layers)

C) AND patient has at least one of the following:

- Purulent drainage from the deep incision.
- Deep incision that spontaneously dehisces, or is deliberately opened or aspirated by a surgeon or other designee AND organism is identified by a culture or non-culture based microbiologic testing method which is performed for purposes of clinical diagnosis or treatment or culture or non-culture based microbiologic testing method is not performed AND patient has at least one of the following signs or symptoms: fever ($>38^{\circ}\text{C}$); localized pain or tenderness. A culture or non-culture based test that has a negative finding does not meet this criterion.
- An abscess or other evidence of infection involving the deep incision that is detected on gross anatomical or histopathologic exam, or imaging test.

Organ/Space SSI

A) An infection occurring within 30 days of the operative procedure (where day 1 = the procedure date).

B) AND infection involves any part of the body deeper than the fascia/muscle layers that is opened or manipulated during the operative procedure.

C) AND patient has at least one of the following:

- Purulent drainage from a drain that is placed into the organ/space (for example, closed suction drainage system, open drain, T-tube drain, CT guided drainage)
- Organisms are identified from fluid or tissue in the organ/space by a culture or non-culture based microbiologic testing method which is performed for purposes of clinical diagnosis or treatment (for example, not Active Surveillance Culture/Testing (ASC/AST)).
- An abscess or other evidence of infection involving the organ/space that is detected on gross anatomical or histopathologic exam, or imaging test evidence suggestive of infection.

D) AND at least one criterion for a specific organ/space infection site listed below

-Gastrointestinal tract infections, excluding, gastroenteritis and appendicitis, must meet at least one of the following criteria:

1. Patient has one of the following:

- a. An abscess or other evidence of gastrointestinal tract infection on gross anatomic or histopathologic exam.
- b. An abscess or other evidence of gastrointestinal tract infection on gross

anatomic or histopathologic exam.

AND organism(s) identified from blood by a culture or non-culture based microbiologic testing method, which is performed for purposes of clinical diagnosis or treatment.

Intraabdominal Infection

1. Patient has organism(s) identified from an abscess or from purulent material from intraabdominal space by a culture or non-culture based microbiologic testing method which is performed for purposes of clinical diagnosis or treatment.
2. Patient has at least one of the following:
 - a. An abscess or other evidence of intraabdominal infection on gross anatomic or histopathologic exam.
 - b. An abscess or other evidence of intraabdominal infection on gross anatomic or histopathologic exam.

AND organism(s) identified from blood by a culture or non-culture based microbiologic testing method, which is performed for purposes of clinical diagnosis or treatment.

3. Patient has at least two of the following: fever ($>38.0^{\circ}\text{C}$), hypotension, nausea, vomiting, abdominal pain or tenderness.

And at least one of the following:

- a. organism(s) seen on Gram stain and/or identified from intraabdominal fluid or tissue obtained during invasive procedure or from an aseptically-placed drain in the intraabdominal space (for example, closed suction drainage system, open drain, T-tube drain, CT guided drainage) by a culture or non-culture based microbiologic testing method which is performed for purposes of clinical diagnosis or treatment.
- b. Organism(s) identified from blood by a culture or non-culture based microbiologic testing method which is performed for purposes of clinical diagnosis or treatment.
- c. *AND* imaging test evidence suggestive of infection (for example, ultrasound, CT scan, MRI, ERCP, radiolabel scans [gallium, technetium, etc.] or on abdominal x-ray), which if equivocal is supported by clinical correlation, specifically, physician documentation of antimicrobial treatment for intraabdominal infection.

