The usage of a wound protector along with wound irrigation intra-operatively is considered standard of care. This study entails utilizing two type of wound protectors, both are considered standard of care in terms of providing the baseline needed protection. Intra-operatively, either CleanCision Wound protector/ irrigation system or Alexis O wound protector will be chosen. Additional wound irrigation and washing with Normal Saline will be performed before skin closure as part of the standard of care. This will include both study groups (patients with Alexis O wound protectors and CleanCision wound protectors). In the CleanCision group, a broad spectrum antibiotic may be added to the irrigation fluid. Post-operatively, patients will be followed for wound infections according to the standard of care in the department of colorectal surgery. For patients undergoing colorectal procedures at the department of colorectal surgery, the timing of outpatient post-operative follow-up can be variable depending on the type of procedure performed, the treating surgeon, the patient place of residence, and the patient general medical condition. To avoid variability, patients will be asked to send a photographic documentation of the wound at day 7 ± 7 days and day 30 ± 7 days postoperatively to the study team. The photographs will be stored in the secure REDCap database. If a patient presents for follow-up at the outpatient clinic at the above time points and as part of standard of care, a photograph of the wound can be obtained during the outpatient visit by the study team member. The purpose of these photographs as well as the time points will be explained to the patient at the time study enrollment. Patients refusing or incapable of sending the photographs will not be enrolled in the study. For study enrolled patients' a reminder will be added to the hospital discharge note asking the patient to send the photographs to the above email address at the corresponding time points.

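### A superficial SSI can count on an unmasked clinician's diagnosis with no required objective finding, and the plan gives the masked photograph reading no power to correct it

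*Combined protocol and SAP*

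**What the plan says.** Section 4.5 adopts WHO definitions based on CDC/NHSN. A superficial SSI must occur within 30 days (A), involve only skin and subcutaneous tissue (B), and meet any one of four alternatives: "C) AND patient has at least one of the following". Three of the four need a finding: purulent drainage, an identified organism, or an untested incision opened deliberately with a sign or symptom. The fourth is "Diagnosis of a superficial incisional SSI by the surgeon or other designee". The exclusions that follow (cellulitis by itself, stitch abscess alone, stab or pin-site infection) limit this alternative but do not require any positive evidence.

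On who knows the arm, section 4.2 says "Intra-operatively, either CleanCision Wound protector/ irrigation system or Alexis O wound protector will be chosen", and blue towels are placed under the protector in control cases only. After surgery, "patients will be followed for wound infections according to the standard of care in the department of colorectal surgery". The only masking is in section 4.3, where the study team member who reads the wound photographs "will be blinded to the type of wound protector used intraoperatively". Section 4.4 takes data from the medical record and lists "The development of SSI per the criteria defined above along with any related investigation / clinical encounter needed for such diagnosis". It has no field for the criterion that was met. No section says how a photograph reading and a chart diagnosis are combined.

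**The concern.** In an open-label device comparison, an outcome that can rest on clinical opinion can move with the opinion-holder's expectations. Expectations are on record here: the Background says participating surgeons credit wound protectors and irrigation with a large role, and that CleanCision could lower SSI rates further. No section requires the diagnosing clinician to be masked or to be someone other than the operating surgeon.

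Masking the person who abstracts the chart, which the plan does not state, would not remove the problem. Someone applying 4.5 as written would still count a recorded diagnosis and pass over an unrecorded one. The sample size rests on incisional SSI, which includes superficial SSI, and few events are expected. A handful of borderline labels could shift the result.

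**Working it through.** **Inputs.** From 3.3: control incisional SSI 4.8%, CleanCision 1.2%, alpha 0.05, 80% power, 351 per arm. Assumed: a two-sided, unadjusted Pearson test, because 3.3 names chi-square and Fisher tests only for preoperative characteristics. Also assumed: the share *s* of SSIs resting on opinion alone and the fraction *w* of those withheld in the device arm. The documents give neither.

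**1. The plan's own figure.** With mean rate 0.030,

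n = [1.960 × √(2 × 0.030 × 0.970) + 0.842 × √(0.048 × 0.952 + 0.012 × 0.988)]² / 0.036² = [1.960 × 0.2412 + 0.842 × 0.2399]² / 0.001296 ≈ 351.3.

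This rounds up to 352 against the stated 351, so the figure reproduces.

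**2. Expected events.** 351 × 0.048 = 16.8 and 351 × 0.012 = 4.2, so about 17 vs 4.

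**3. How far the result rests on opinion-only cases.** Use z = (difference in proportions) / √[p̄(1 − p̄) × 2/351], where p̄ is total events / 702. For illustration take s = 35%: 0.35 × 17 ≈ 6 control events and 0.35 × 4 ≈ 1 device event.

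| Events, control vs device | Difference | z | p |
|---|---|---|---|
| 17 vs 4 (all counted) | 13/351 = 3.7 points | 2.88 | 0.004 |
| 11 vs 3 (same share removed from both arms) | 8/351 = 2.3 points | 2.16 | 0.031 |
| 11 vs 4 (control events only removed) | 7/351 = 2.0 points | 1.83 | 0.068 |

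**4. False-positive risk with no true effect.** Set the control rate at 0.048 and the recorded device rate at 0.048 × (1 − f), where f is the fraction of all device-arm SSIs not labelled. Sum the binomial probabilities of every pair of counts with z > 1.96 in favour of CleanCision.

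| Assumption | f | Recorded device rate | Chance of significance favouring CleanCision |
|---|---|---|---|
| No bias | 0 | 4.80% | 2.5% |
| s = 35%, w = 20% | 0.35 × 0.20 = 0.07 | 4.46% | 4.1% |
| s = 35%, w = 30% | 0.35 × 0.30 = 0.105 | 4.30% | 5.1% |
| 20% of all device-arm SSIs withheld | 0.20 | 3.84% | 9.1% |
| 30% of all device-arm SSIs withheld | 0.30 | 3.36% | 15.9% |

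**5. What the last two rows require.** If only opinion-only cases can be withheld and s = 35%, then f = 0.20 needs 0.20/0.35 = 57% of them withheld, and f = 0.30 needs 0.30/0.35 = 86%.

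**The case against.** The strongest reply is that this is a recognised surveillance definition, adopted deliberately, and that it has limits. The red, warm, swollen wound, which is the obvious borderline case, does not qualify by itself. Deep SSIs, and superficial ones with recorded pus or an organism, count whatever the surgeon thinks. This stands. It is why the definition should be kept for the main count, and why the exposed share is smaller than all incisional SSIs. It does not remove the gap, because the exclusions rule cases out without requiring evidence to rule one in.

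A reader might infer that the operating surgeon makes the diagnosis. The text says surgeon or other designee, so this is plausible but not stated. It does not even say whether the photograph reader could be a designee. What the documents support is that nothing requires the diagnosing clinician to be masked or different from the operator.

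A reader might also infer that opinion-only cases could never be identified afterwards. That goes too far. Section 4.4 records related investigations, encounters, progress notes and timing, and photographs are stored. Some cases could be reconstructed, but only partly, because a bare diagnosis may leave nothing to trace.

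Finally, the other criteria also depend on clinicians, for example "Superficial incision that is deliberately opened by a surgeon or other designee and culture or non-culture based testing is not performed". That is true, but only the diagnosis alternative needs no finding at all.

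**Conclusion.** The concern holds as a limited but real route to bias: unmasked opinion can add or withhold some superficial SSIs, and the plan does not let its one masked assessment correct this. On the assumptions shown, the one-directional false-positive chance rises from 2.5% to about 4% to 5% when only an assumed 35% opinion-only share is exposed.

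It is tempting to quote 9% to 16% as the expected inflation. The documents do not support that. Those figures need 20% to 30% of all device-arm SSIs to go unlabelled, including cases that count regardless of opinion. Nor do the documents show that the planned result would lose significance. At 11 vs 3 it stays below 0.05 under Pearson, and the loss at 11 vs 4 depends on removing control events only. All of these results depend on the assumed shares and the assumed test. This is a cheap improvement that should be made, not a flaw that invalidates the design.

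**What to change.** Keep the WHO/NHSN definition for the main count.

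1. In 4.4 C, add a REDCap field recording which 4.5 criterion or criteria each superficial SSI met, completed prospectively.
2. In 3.3, pre-specify a sensitivity analysis, applied identically in both arms. It drops superficial SSIs that rest only on the diagnosis criterion unless the masked photograph reader also called SSI. It adds patients whom the masked reader called SSI but who have no chart diagnosis. The second part is essential, because dropping cases cannot recover events that were withheld. Since 4.2 allows the second photograph up to day 37 (30 + 7), state how a call on a photograph taken after the 30-day window is handled.
3. Tabulate photograph and chart disagreements by arm. Report the main and sensitivity differences with 95% confidence intervals, and describe a benefit as robust only if the two estimates are similar in size. Agreement in direction is too weak a test, since 11 vs 4 still points the same way as 17 vs 4.

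The cost is one field and one extra analysis on photographs already planned, with no change to the endpoint definition, sample size or care. The downside is fewer events and a wider interval in the sensitivity analysis if opinion-only cases are dropped.

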5. ADVERSE EVENTS

5.1 Definition

An **adverse event** (AE) is any unfavorable or unintended event, physical or psychological, associated with a research study, which causes harm or injury to a research participant as a result of the participant's involvement in a research study. The event can include abnormal laboratory findings, symptoms, or disease associated with the research study. The event does not necessarily have to have a causal relationship with the research, any risk associated with the research, the research intervention, or the research assessments.

Adverse events may be the result of the interventions and interactions used in the research; the collection of identifiable private information in the research; an underlying disease, disorder, or condition of the subject; and/or other circumstances unrelated to the research or any underlying disease, disorder, or condition of the subject.

5.2 Reporting Adverse Events

Although we do not anticipate any serious adverse events, all reportable serious adverse events will adhere to the policy guidelines of the IRB and the sponsor, if applicable. All other adverse events associated with surgery in the 30 day post-operative setting will be recorded on an adverse event log and submitted to the Cleveland Clinic IRB on an annual basis.

